# **Hypothesis:**

- 1. That maternal and childhood helminth infection reduce the effectiveness of childhood immunisations.
- 2. That helminth infection increases susceptibility to viral and bacterial infectious diseases.
- 3. That treatment of maternal and childhood helminth infection can improve the effectiveness of childhood immunisations and reduce the incidence of infectious diseases in childhood.

#### **Specific Aim:**

To examine the impact of helminths on the response to immunisation, and on susceptibility to infectious diseases in childhood, in a cohort of 2500 mothers and their children in Entebbe, Uganda. The study will have three randomised, placebo-controlled comparisons as well as observational components.

1. To examine the effects of maternal infection with intestinal nematodes, and of the treatment of maternal nematode infection in pregnancy. Mothers will be randomised to receive treatment with albendazole or placebo during the second to third trimester of pregnancy.

Mothers who are severely anaemic (haemoglobin  $\leq 8g/dl$ ) will be excluded from randomisation and treated with albendazole.

2. To examine the effects of maternal schistosomiasis, and of the treatment of schistosomiasis in pregnancy. Mothers will be independently randomised to receive treatment with praziquantel or placebo during the second to third trimester of pregnancy.

Mothers who have persistent diarrhoea with blood in the stools will be excluded from randomisation, investigated, and treated for schistosomiasis if present.

Thus the study will comprise four groups of mothers, according to treatment during pregnancy: (1) treated with both albendazole and praziquantel; (2) treated with only albendazole; (3) treated with only praziquantel; (4) no anti-helminthic treatment.

All mothers will have a second stool sample taken at delivery. All mothers will be mass treated with albendazole and praziquantel after delivery.

- **3.** To examine the effects of acquisition of intestinal nematodes during childhood and of regular mass treatment in childhood. After one year of age, children will be randomised to receive albendazole or placebo every 3 months. All children will receive annual, selective treatment based on stool analysis.
- **4.** To examine the effects of childhood schistosomiasis. This component will be observational. Children will receive annual, selective treatment based on stool analysis.

**Co-infections other than helminths may also have immunomodulating effects.** As an additional objective we will use stored samples from the cohort to examine the effects of herpes virus infections. Protocol amendment, January 2009. This component will be observational. Stored sera will be used to determine the age of first infection with Herpes simplex and cytomegalovirus. Particular attention will be paid to the relationship between these infections and the immune response following BCG, and the risk of TB infection.

#### The principal outcomes will be:

(1) immunological responses to childhood immunisations (BCG, tetanus and measles)

(2) immunological responses to HIV in children of HIV-1 infected mothers

(3) the incidence of infectious diseases in childhood (pneumonia, diarrhoea, measles, malaria, tuberculosis disease and tuberculosis infection (protocol amendment, January 2009) and vertical transmission of HIV infection).

#### **Background**

Infectious diseases are the most important cause of illness and premature death in Africa today. Pneumonia, diarrhoea, measles and malaria are the leading causes of death in young children. Tuberculosis and HIV infection are the leading causes of death in adults. In addition, African populations have a very high prevalence of helminth infection. Over 150 million are thought to be affected by schistosomiasis, and intestinal nematodes are even more widespread. Most helminth infections can be treated easily, but they are often ignored, because the effects are unnoticed by the human host. This occurs partly because helminths have a profound effect on the host immune response, which allows parasites to persist for long periods, with relatively little damage to host tissues. However, recent studies, including our own, indicate that the effect of helminths on the immune response extends to other pathogens, and may markedly impair protective responses, especially to intracellular pathogens, such as *Mycobacterium tuberculosis*, and to viral infections, including the Human Immunodeficiency Virus (HIV). Similarly, helminth infection may impair the immune response to vaccine antigens. This is a particularly intriguing possibility in relation to Bacille Calmette-Guerin (BCG) immunisation, which has variable efficacy, correlated to distance from the equator and hence with the global distribution of helminth infections. Thus helminths may influence susceptibility to other pathogens directly, or through their effect on vaccine-induced immunity, and treatment of helminth infections may resolve these effects.

A role for helminths in susceptibility to other pathogens is suggested by current understanding of the type 1/ type 2 dichotomy of the immune response. In essence, type 1 responses are characterised by production of gamma interferon IFN-y, promote macrophage and cytotoxic T-cell activation, and contribute to protection against intracellular pathogens. In mice, type 1 responses also stimulate production of the opsonising and complement fixing sub-classes of antibodies required for protection against extracellular microbes, but in humans this function has not been proven. Type 2 responses are characterised by production of IL-4, IL-5, and IL-13, and of antibodies including immunoglobulin (Ig)E, and eosinophilia. Mycobacterial and helminth antigens induce highly polarised type 1 and type 2 responses, respectively. Other antigens elicit more balanced, mixed responses, and mixed responses also occur in the early phases of lymphocyte activation and in some subsets of memory T-cells. The character of the immune response to a specific antigen may be influenced by the initial, non-specific cytokine response, or the pre-existing cytokine milieu. For example, type 1 responses can be initiated by IL-12 production from macrophages or by interferons released from somatic cells following viral infection. Type 2 responses may be promoted by release of IL-4 from basophils or CD4+NK1+ T-cells. Type 1 and type 2 responses are mutually antagonistic so that an initial type 1 or type 2 bias in the response is likely to be sustained. Thus, by inducing a type 2 bias, helminths may impede development of protective type 1 responses to bacterial and viral pathogens.

In addition, helminths have evolved a broad array of mechanisms to evade host immune defences, several of which may modulate the immune response to other pathogens. Of particular interest in relation to T-cell mediated immune responses are effects which impair antigen presentation or macrophage activation. These functions may be inhibited by molecules, such as phosphocholine and protease inhibitors, secreted by helminths. In addition, cytokines such as IL-10, induced by helminth infection, can inhibit macrophage activation and down-regulate expression of antigen presenting molecules and co-stimulatory molecules for both type 1 and type 2 T-cells. Similarly, tissue growth factor (TGF)- $\beta$  can inhibit macrophage killing of both intracellular and extracellular organisms. Other mechanisms may influence the response to extracellular pathogens. Parasites secrete molecules which can degrade antibodies, interfere with complement activity, inhibit neutrophil chemotaxis and inhibit the oxidative activity of activated leukocytes.

Studies in mice demonstrate that helminth infection can lead to down regulation of type 1 responses, or a switch to a type 2 response, to unrelated antigens. Prior infection with

Schistsoma mansoni reduces type 1 responses to unrelated antigens, and delays clearance of viral infection. Prior exposure to filarial antigen induces a switch to a type 2 response to mycobacterial antigens. Prior infection with *Fasciola hepatica* suppresses the type 1 response to *Bordetella pertussis*, and leads to more severe bacterial disease. Furthermore, infection with *Fasciola* after exposure to *B. pertussis* leads to suppression of an established type 1 response. Thus helminth infection can influence both induction and effector components of the type 1 immune response, and increase susceptibility to bacterial and viral pathogens. Interestingly, the potency of the effect of helminth co-infection is further illustrated by studies which suggest that helminth infection ameliorates disease mediated by type 1 responses: co-infection with helminths reduces gastric atrophy induced by *Helicobacter felis*, despite the presence of high numbers of bacteria, and protects against development of diabetes in genetically predisposed mice.

There is evidence that helminth infection modulates responses to unrelated antigens, and influences susceptibility to infectious diseases in humans, also. Reduced responses to unrelated, delayed hypersensitivity, skin test antigens have been demonstrated in individuals with helminth infection. Results with respect to cytokine production have been more variable. Some studies have shown a reduction in type 1 responses specific for parasite antigens. Others, including our own, have shown suppression of IFN-y responses to unrelated antigens, but not necessarily a switch to a type 2 profile. More recently, we demonstrated marked suppression of IFN- $\gamma$  responses to M. tuberculosis antigens following activation of parasite specific responses by treatment for S. mansoni in HIV-1 infected subjects, while IL-2 and IL-5 responses to M. tuberculosis antigens showed a transient rise (Appendix 1, Figure 3). Results may vary between studies for technical reasons, such as use of separated cells rather than whole blood assays, the latter being more likely to retain parasite antigens, or parasite induced lymphokines. Alternatively, in some studies there may have been differences in exposure to unrelated antigens between helminth infected and control subjects, or differences in the sequence of exposure to helminths and unrelated antigens. Studies of the effect of helminths on the outcome of immunisation are helpful in this respect, and several of these demonstrate impairment of cellular responses. These immunological findings have led us to the central question of this proposal, which is whether helminths are also associated with increased susceptibility to bacterial and viral disease. Our data, so far, indicate that this may be so in HIV-1 infected subjects. In one study, eosinophilia, which may represent a type 2 bias or be a marker of helminth infection, was associated with a high risk of progression to active tuberculosis. In another study, activation of the parasite specific response to S. mansoni after treatment was associated with a transient increase in HIV load (Appendix 1, Figure 1) and persistent helminth infection seemed to be associated with more rapid HIV progression (Appendix 1, Figure 2). On the other hand, helminths may also ameliorate disease in humans in some situations. Of particular interest for the proposed study is evidence that helminth infection may be associated with less severe malaria; if so, a detrimental effect of helminths on bacterial or viral infection may be offset by a reduced incidence of severe malaria. Helminth infection may also be associated with reduced expression of atopic disease, perhaps because effector mechanisms are suppressed.

**Exposures in utero and in early neonatal life may have lifelong effects.** This has been illustrated for immunological responses by studies suggesting that exposure to viral and bacterial pathogens early in life leads to a lower risk of atopic disease. Similarly, our own findings in HIV-1 infected adults in Uganda, supported by data from school children in Brazil, suggest that BCG immunisation may have a long term influence on susceptibility to helminths. Both these observations suggest a potent effect of exposures which induce type 1 responses in infancy. Our hypothesis proposes that helminth infection has an equally important converse effect, suppressing type 1 responses in infancy. Helminth infection is rare in infants, but maternal helminth infection can sensitise neonates by exposure to helminth antigen, or to maternal anti-idiotype antibody, which may mimic antigen. Thus it has been shown that children of mothers with microfiladermic onchocerciasis have increased type 2 responses to parasite antigens and reduced type 1 responses to

non-parasite antigens and that children of mothers with schistosomiasis or filariasis have a reduced IFN- $\gamma$  response following BCG immunisation. These studies emphasise how maternal helminth infection may influence induction of immunity by vaccines given in the first weeks of life.

**Together these findings show that helminth infection may have an important effect on susceptibility to infectious disease in the tropics.** This possibility needs to be explored further at several levels. First, as discussed, type 1/ type 2 switching is unlikely to be the only mechanism of interaction between helminths and other pathogens. Second, few studies have examined the effects of intestinal nematodes, although these are more widely distributed than schistosomiasis and filarial infections; thus key findings need to be re-examined for intestinal nematodes. Third, the effect of treatment of helminths, and the time course of changes in immune responses to unrelated antigens, need to be explored. Finally, the immunological correlates of protective immunity against many pathogens, including *M. tuberculosis* and HIV, are still uncertain, and immunological studies alone fail to determine the effect of helminths on the actual efficacy of vaccines, and incidence of infectious disease. We now aim to investigate these issues in the studies described in this proposal.

#### **Experimental Design and Methods:**

Setting and facilities. The studies will be conducted at the Entebbe Hospitals. The surrounding community has a strong Local Council administration, with over 20 units in the Entebbe Municipality (including the part of Katabi which belongs in the municipality) and 50-60 if the adjacent area of Katabi is added. Laboratory investigations will be done at the Uganda Virus Research Institute (UVRI) where facilities for haematology, serology, bacteriology, parasitology and mycobacterial diagnosis, as well as cell culture, ELISA, PCR and flow cytometry are in place. The studies will build on our collaborations with the Medical Research Council Programme on AIDS, the Uganda National Tuberculosis Control Programme, the Uganda Vector Control Programme, [name] (Department of Pathology, University of Cambridge), [name] (Imperial College, London) and the Immunology and Tropical Epidemiology Groups, London School of Hygiene & Tropical Medicine.

#### Establishing the cohort.

The cohort will be recruited at the Entebbe General Hospital. If necessary, recruitment can be extended to the Private Wing also. Each year, 1200-1500 deliveries take place. About 70% of the mothers who deliver in the General Hospital live in Entebbe Municipality and Katabi, and over 90% of these attend the Hospitals' antenatal clinics before delivery (Appendix 2A). The proposed study profile is summarised in Appendix 3.

#### **Procedures**

#### Mothers: enrolment visit.

Women will be invited to participate in the study at their first antenatal visit if their normal residence is in the proposed study area (Entebbe Municipality; women from the additional, adjacent part of Katabi will be included later if necessary to maintain recruitment rates). Mothers who feel unable to decide to join the study at their first visit to the antenatal clinic, but who wish to do so at later visits, will be accepted provided that they accept all the study procedures, particularly the need for a blood draw on the day of screening.

They will be excluded if they have a history of adverse reactions to anti-helminthic drugs.

They will be excluded if, in the opinion of the doctor or midwife, the current pregnancy is not normal. Normal pregnancies would include twins. Abnormal pregnancies would include, for example, those in which the mother has gestational diabetes, pre-eclampsia or vaginal bleeding.

They will be excluded if they have already participated during an earlier pregnancy within the duration of the study. (Inclusion of more than one pregnancy and child for the same mother would complicate analysis, and the mother's behaviour with regard to antenatal care and use of antihelminthics for herself and her child might be influenced by earlier participation in the study.)

They will be asked to give informed consent for participation in the study of albendazole in pregnancy, and for follow up of the babies to one year of age.

A questionnaire regarding demographic and socio-economic details, clinical history and examination will be completed.

They will have blood drawn for full blood count, malaria slide, examination for microfilariae, HIV and syphilis serology and studies of the maternal immune response (30 ml).

Urine will be examined for protein and glucose using a dipstick.

They will be asked to provide a stool sample.

They will be provided with haematinics and antimalarial prophylaxis (an initial dose of Fansidar). Women with positive syphilis serology (RPR and TPHA) will be treated.

Tetanus immunisation will be given.

In keeping with government policy, mothers will be encouraged to receive their HIV result and this study will be integrated with the Ministry's programme for Prevention of mother-to-child HIV transmission. For mothers who agree, pre- and post- HIV test counselling will be given and HIV serology will be performed using a rapid testing algorithm. HIV-positive mothers will be offered nevirapine and advised on infant-feeding practices. Those wishing for specific follow up care will be referred to TASO Entebbe, to the Mildmay Centre, or to appropriate clinics elsewhere, according to their preference.

Protocol amendment, 14th March 2005. In view of the introduction of provision of antiretroviral therapy at Entebbe Hospital, mothers who are HIV-positive will be offered a repeat full blood count and CD4 T cell count to determine whether referral for treatment is indicated. Those who are treated will have full blood count and CD4 T cell count repeated every six months. Those for whom anti-retroviral treatment is not yet indicated will have repeat CD4 counts performed at intervals of six months to one year, to allow referral when necessary. Remaining material from the 5 ml sample will be stored for possible future virological studies.

Mothers: randomisation to albendazole or placebo and to praziquantel or placebo/ no praziquantel. Women will be requested to return to the clinic with a stool sample.

On receipt of the stool sample (but before analysis of stool results) they will be randomised to receive albendazole (a single dose of 400 mg) or placebo and to praziquantel (a single dose of 40 mg/kg) or placebo/ no praziquantel.

If the first trimester is not yet complete administration of the study drugs will be delayed. The mother will be given an appointment to return during the second trimester to receive the drugs. It is expected that this will only be necessary in a minority of cases.

Women with severe anaemia (haemoglobin  $\leq 8g/dl$ ) will be excluded from randomisation and will be treated with albendazole, because of the known benefit of treatment of hookworm, if present. If indicated, additional measures will be taken for management of anaemia. Women with persistent diarrhoea with blood, which might be caused by schistosomiasis, will be excluded from randomisation and will be investigated, and treated for schistosomiasis if present.

Mothers: six weeks after enrolment. Protocol amendment, March 2003. "Effect of praziquantel treatment during pregnancy on anti-schistosome immune responses in pregnant women and their infants." All mothers will be requested to provide a second stool sample and a second blood sample (maximum 30 ml) to allow evaluation of the effects of treatment during pregnancy at a

consistent interval after treatment. This is particularly pertinent to the study of the effects of treating schistosomiasis.

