#### Mothers: at delivery.

A second blood (20 ml), urine and stool sample will be obtained at delivery, before the mother leaves hospital. The blood samples will be used to perform a full blood count (for assessment of post-partum anaemia) a malaria slide and studies of the maternal immune response. The urine sample will be used as part of the assessment of pre-eclampsia and eclampsia. The stool sample will be used to determine the presence of persisting helminth infections, and to guide treatment in the case of *Strongyloides*. A placental smear will also be examined for malaria. Mothers found to have malaria will be treated.

After delivery, participants will be taken home if possible, to ensure follow up.

Mothers who receive the study drugs but do not deliver the baby in the hospital will be followed up at home to determine the outcome of the pregnancy.

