#### APPENDIX 3: The impact of helminths on the response to immunisation and on susceptibility to infectious diseases in childhood in Uganda. Proposed Study Profile.

First visit to the antenatal clinic.

• Women who live in study area; no history of adverse effects of anti-helminthics.

Т

- Consent to study of treatment in pregnancy.
- Screening investigations, including Hb, HIV, RPR, immunological studies.
- Provision of antimalarials and haematinics.
- Request stool sample.

	↓
On receipt of stool sample; gestation > 14	weeks; screening Hb results available.

 
Severe anaemia:
 
Treat with albendazole; exclude
 
Persistent diarrhoea with blood:
 
investigate and treat; exclude
 
	
 
Not severe anaemia:
 
Randomise to albendazole or placebo & praziquantel or placebo
 

At delivery.	

 
Mother:
 
Blood and stool samples
 
Nevirapine if known HIV+
 
	

Child:

Cord blood

Nevirapine if mother known HIV+

Post delivery.	↓
• Mass treatment with albendazole and praziquantel; selective treatment for Strongyloides .	• 1-2 samples post immunisation for studies of time course of immune response in selected participants.
	 ▼
	At one year.
	
 
Blood and stool samples
 
Specific treatment for worms found
 
Consent to study of treatment in childhood.
 
Randomisation to receive albendazole or placebo at 3 month intervals, starting at age 15 months
 

	Annual visits.
	Blood and stool

- Blood and stool
- Specific treatment for worms found

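### The repeat maternal sample is timed from enrolment although its purpose needs a fixed interval from treatment, and first-trimester deferral of the drug separates the two

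*Protocol*

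**What the plan says.** The March 2003 amendment in the Procedures section asks every mother for a second stool and blood sample. Its heading sets the time: "Mothers: six weeks after enrolment". Its text sets the purpose, which is to evaluate treatment in pregnancy at a "consistent interval after treatment. This is particularly pertinent to the study of the effects of treating schistosomiasis".

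The protocol then places enrolment and dosing as follows.

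- **Procedures, "Mothers: enrolment visit".** "Women will be invited to participate in the study at their first antenatal visit"; joining at a later visit is also accepted. Baseline blood, including the malaria slide, is drawn here. Appendix 7 refers to a malaria film at enrolment, which fits this visit.
- **Procedures, randomisation of mothers.** "Women will be requested to return to the clinic with a stool sample". No time limit is set for that return. Randomisation follows receipt of the stool. Then: "If the first trimester is not yet complete administration of the study drugs will be delayed", with a second-trimester appointment for dosing. This is expected for a minority. Appendix 7 ends the first trimester at 14 weeks.
- **Appendix 3.** The step containing randomisation is headed "On receipt of stool sample; gestation > 14" weeks.
- **Appendix 8.** Being enrolled in the trial means the occasion when the stool is brought and the numbered drug envelope is handed over.
- **Procedures, post-delivery treatment.** The same amendment takes blood from mothers with schistosomiasis before the post-delivery treatment, and stool and blood six weeks later, to compare treatment in pregnancy with treatment after delivery.
- **Procedures, at delivery.** "Mothers who receive the study drugs but do not deliver the baby in the hospital will be followed up at home" to learn the pregnancy outcome.

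**The concern.** The sample is meant to show clearance of infection and change in immune response at a known time after treatment. A visit counted from enrolment does that only if the drug is given on the enrolment day, or after the same delay in every woman. As the Procedures section describes it, neither holds: dosing waits for a stool sample with no return window and, in early pregnancy, for the second trimester.

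Three things are at stake. The drug-versus-placebo contrast at this time point would mix different exposure times. The planned comparison with treatment after delivery would set a sample timed from enrolment against one timed from treatment. And if women are randomised when the stool arrives but dosed later, some may be randomised and never dosed, while home tracing of pregnancy outcome is promised only to those who receive the drugs.

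**Working it through.** The plan gives no figure to reproduce here; only timing arithmetic applies.

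**Inputs from the protocol.** The sample falls 6 weeks after enrolment. The drug is not given before 14 weeks' gestation (deferral rule in Procedures; trimester limits in Appendix 7).

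**Not given, so varied or assumed.** g is gestation in weeks at enrolment; no lower limit is stated. L is the lag in weeks from enrolment to stool return, taken as 0, 1, 2 or 4. Deferred women are assumed to be dosed as soon as they reach 14 weeks; a later appointment shortens the interval further.

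**Meaning 1: enrolment is the first antenatal visit.** The drug is given max(L, 14 - g) weeks after enrolment, so

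drug-to-sample interval = 6 - max(L, 14 - g).

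| g at enrolment | L = 0 | L = 1 | L = 2 | L = 4 |
|---|---|---|---|---|
| 6 | -2 | -2 | -2 | -2 |
| 8 | 0 | 0 | 0 | 0 |
| 10 | 2 | 2 | 2 | 2 |
| 12 | 4 | 4 | 4 | 2 |
| 14 or more | 6 | 5 | 4 | 2 |

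Entries are weeks from drug to sample; a negative entry means that the sample comes first. For example, g = 10 with L = 0 gives 6 - (14 - 10) = 2. For women at 14 weeks or more the interval is 6 - L.

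**Meaning 2: enrolment is the stool-return visit (Appendix 8).** L drops out, g is gestation at that visit, and the L = 0 column applies. Women past the first trimester are sampled at 6 weeks. Deferred women still get 6 - (14 - g): 4 weeks at g = 12 and 2 at g = 10.

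**Effect on the randomised contrast.** Neither g nor L depends on the arm. Active and placebo arms therefore share the same spread of intervals. A woman on active drug who is sampled before dosing shows no drug effect, and one sampled early may show a different effect from one sampled at 6 weeks. The result is dilution and added noise, not a difference between arms that would arise without a drug effect.

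**Effect on the comparison with post-delivery treatment.** The post-delivery sample is 6 weeks after treatment. The pregnancy sample is 6 - max(L, 14 - g) weeks after it, which is equal or shorter and never longer. The discrepancy runs in one direction.

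**Randomisation and follow-up.** The Procedures section randomises at stool receipt and delays only the drug. Appendix 3 shows randomisation with gestation already above 14 weeks. Appendix 8 hands over the envelope at stool return. Only the Appendix 3 order removes the deferral gap between allocation and drug. With that gap, a randomised woman who is never dosed and delivers outside the hospital has no stated route to outcome capture.

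**With the sample tied to dosing.** The interval is 6 weeks for every woman, whatever g and L are.

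**The case against.** The strongest reply is that Appendix 8 equates enrolment with the visit at which the drug is handed over. Most women would then be sampled six weeks after dosing, and if Appendix 3 also governs, so that nobody is enrolled until past 14 weeks, the lag disappears. The amendment's text also tells staff what the interval is for. This stands in part: on the Appendix 8 meaning the problem shrinks to deferred women. It does not vanish, because the Procedures section randomises on stool receipt and defers only the drug, and the enrolment-visit heading and Appendix 7 use the word for the first visit. A stated purpose is not a scheduling rule.

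It is also fair that the sample serves an added sub-study. The scheduled analyses of maternal immune response compare enrolment with delivery, and delivery stool also measures persisting infection. That limits the consequence to this time point and its comparisons.

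The preliminary data in Appendix 1 are weak evidence of harm. They show responses at 5 weeks that differ from those at 4 months in HIV-positive adults, with 13 *S. mansoni*-only subjects having complete CD4 and viral load data. They show that time since treatment matters, but not how responses differ between, say, 4 and 6 weeks.

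A reader might infer that undosed women drop out of the intention-to-treat pregnancy outcomes. The protocol does not say so. The delivery section limits only home tracing after a non-hospital birth; undosed women who deliver in hospital are still recorded, and nobody is excluded from analysis.

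**Conclusion.** The timing rule does not secure the interval that the amendment says it needs. On either meaning of enrolment, deferral cuts the interval for a minority of women, to at most 4 weeks at g = 12 and 2 weeks at g = 10. On the first-visit meaning, the stool-return lag cuts it for others as well: 2 to 5 weeks for assumed lags of 4 to 1 weeks. The first consequence is dilution of the drug-versus-placebo contrast at this sample; the second is loss of comparability with the post-delivery sample.

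Two stronger readings are not supported. One is that women are known to be sampled before the drug: with dosing at 14 weeks this needs g below 8, which the protocol permits, but it gives no gestation distribution. The other is that the arms are biased against each other: the lag is the same in each.

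The conflict over when randomisation takes place, and the limit on home follow-up to women who receive the drugs, are both in the text. How many women they affect cannot be computed from the protocol.

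**What to change.** 1. Define enrolment once and use it in that sense in Procedures and in Appendices 3, 7 and 8.
2. Retitle the visit and time it six weeks after the date on which study drug or placebo is taken. This adds no visits or samples; only the scheduling date and wording change.
3. Reconcile the randomisation text in Procedures with Appendices 3 and 8, stating whether the numbered envelope is allocated at stool receipt or only once the woman can be dosed. This is a wording change.
4. Extend home follow-up for pregnancy outcome from women who receive the study drugs to all randomised women. The cost is some extra home visits, for undosed women who deliver outside the hospital.
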